Study Title: Does the use of continuous glucose monitoring (CGM) in the immediate postpartum period in women with pregestational diabetes admitted to the hospital decrease hypoglycemic episodes?

NCT number: 06141941

Date: January 1, 2023

PI: [name]

Research hypothesis:

The use of continuous glucose monitoring (CGM) to monitor glucoses in patients hospitalized in the immediate postpartum period is more effective at identifying patients with hypoglycemia than the traditional point of care (POC) blood glucose testing.

Population: pregnant women with type 1 or type 2 diabetes

Inclusion criteria: Pregnant women with type 1 or type 2 diabetes managed with insulin, who own a smart device (which will serve as a receiver for the CGM device).

Exclusion: patients less than 18 years of age, non-English speaking patients, gestational diabetes, extensive skin changes/diseases that inhibit wearing a sensor on normal skin, known allergy to adhesives

Number of subjects proposed to complete this study:

This is a pilot study to evaluate the role of a CGM device to decrease hypoglycemic events in hospitalized patients in the postpartum period, a power analysis has not been pre-specified.

30 patients were chosen as this appears to be attainable number based on the number of DM1/DM2 pregnant patients which are seen in the high-risk OB clinic.

Patient recruitment:

Pregnant patients with type 1 or type 2 diabetes managed with insulin will be approached during their OB clinic visit during the third trimester prior to 28 weeks, to describe the study and assess if they would be interested in participating. If they meet inclusion criteria and opt to enroll in the study, they will be consented during that visit. If patients would like time to discuss study with family/friends, they will be given up until the time of delivery (~10-12 weeks) to determine if they would like to participate in the study. During the consenting process, patients will be aware that participation in this study will not have any effect on routine standard of care.

If patients opt to enroll in the study, a CGM device will be placed by research personnel during their clinic visit if seen within 3 days of their planned induction of labor or planned cesarean section. If a patient is not seen for a prenatal visit 3 days prior to their delivery (i.e. missed clinic appointment), the device will be placed upon arrival to L&D for delivery. Patient will be assisted in getting the Dexcom G6 app on their cell phone to be the receiver of glucose data.

Patients who are currently using the Dexcom CGM for routine monitoring of their glucoses, will be allowed to continue using their own sensor and transmitter. Upon presentation to Labor and Delivery, patients will be assisted in activating the Share App on their cell phone.

Labor and Delivery Nursing Staff will be given a Samsung phone with the Follow app in order to receive glucose data. The Samsung phone will be transferred to the Mother/Baby Unit with the patient after delivery.

CGM sensors and transmitters will be kept locked in the MFM offices in a secure file cabinet. Study personnel will have a key to the file cabinet and access to the devices. Upon arrival of a study

patient to labor and delivery, study personnel will remove a sensor and transmitter from the secure file cabinet in order to place the CGM on the patient.

Glucose values from the CGM device will then be available to nursing through the Samsung phone. Nursing will be able to see current glucose data on their patient and would receive alarms to indicate hypoglycemia or impending hypoglycemia. Nursing will be provided with instructions for how to access the CGM follow app and how to appropriately respond to the alarms. Nursing will continue to perform standard POC blood glucose monitoring per routine protocol but will also obtain a finger stick to validate a blood glucose level whenever a low CGM alarm sounds. Low blood glucose values <70 mg/dl will be treated per hospital nursing policy. Monitoring of glucose levels through the CGM device will continue throughout the postpartum hospital stay. Patients who do not use CGM as part of their routine care, will have their CGM sensor and transmitter removed prior to discharge from the hospital.

Following discharge from the hospital, there will be no additional long-term follow-up.

Participants will be provided compensation of \$25 e-voucher upon completion of the study and discharge from the hospital. The e-voucher is provided through University Accounting Services.

Data collection and analysis:

Data variables to be collected include the type of diabetes (DM1/DM2), POC glucose values, number of hypoglycemic events, number of times treated for hypoglycemia.

Subjects will be de-identified with the use of a separate document correlating subjects medical record number with the study ID number. The study data will be entered into a REDCap database. At the conclusion of the research project, the key will be destroyed.

With DEXCOM CGM services, glucose values will be uploaded to a DEXCOM password protected website to see glucose values in real time.

Continuous variables will be analyzed using a fishers exact t-test (i.e. blood sugar measurements). Categorical variables will be compared using a chi square analysis (i.e. hypoglycemic events). $P < .05$ will be considered statistically significant.

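### The title and sample-size section aim at a decrease in hypoglycemia, but every patient has alarmed CGM and no comparator is described, so a decrease cannot be concluded

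*Combined protocol and SAP*

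**What the plan says.** The combined protocol and SAP states its purpose in three places, and they do not agree.

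- The Study Title asks whether CGM use in the immediate postpartum period will, "in women with pregestational diabetes admitted to the hospital decrease hypoglycemic episodes".
- The section on the number of subjects repeats that aim: "This is a pilot study to evaluate the role of a CGM device to decrease hypoglycemic events in hospitalized patients in the postpartum period". It adds that "a power analysis has not been pre-specified" and that "30 patients were chosen as this appears to be attainable number".
- The Research hypothesis is different: CGM "is more effective at identifying patients with hypoglycemia than the traditional point of care (POC) blood glucose testing".

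The procedures under Patient recruitment describe one way of handling everyone who enrolls. "If patients opt to enroll in the study, a CGM device will be placed by research personnel during their clinic visit" when that visit falls close enough to a planned delivery; otherwise the device goes on at arrival for delivery. Women already using this CGM brand "will be allowed to continue using their own sensor and transmitter". Nursing sees the readings and "would receive alarms to indicate hypoglycemia or impending hypoglycemia". Routine POC testing continues in the same women, and each low alarm prompts an additional confirmatory finger stick.

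Under Data collection and analysis, the variables are diabetes type, POC values, a count of hypoglycemic events and a count of treatments. Events are to be compared by chi-square at P < .05. The section does not name the groups or methods being compared, or say which detection source feeds the event count.

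**The concern.** Whether CGM reduces hypoglycemia and whether CGM finds more of it are separate questions. The first needs an estimate of how many episodes would have occurred without CGM. The second needs two detection methods applied to the same women. The procedures resemble the second design, while the title and the sample-size section promise an answer to the first.

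The event count is also caught between two mechanisms. Extra finger sticks after alarms reveal low values that scheduled testing would have missed, which pushes the count up. Warnings of impending hypoglycemia may let staff act before a low value occurs, which pushes it down. A single total cannot separate the two. At stake is the study's headline conclusion: with an aim worded as a decrease and a significance threshold in place, a reader of the results would expect a statement about reduction that the data cannot support.

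**Working it through.** **1. The plan's own figure.** The only design number is 30 patients, chosen because it is attainable. No event rate, effect size, power or allocation ratio is given, so there is nothing to reproduce.

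**2. Is there a contrast that could show a decrease?** The documents describe no randomization, POC-only group, historical cohort, masked-CGM period or pre-CGM baseline. The continuing POC tests are taken in women who are already managed with CGM alarms. They therefore do not show what would have happened without CGM. On its own, a group of 30 yields a proportion with its interval: if 9 of 30 had an event (assumed), that is 30%, with an exact 95% interval of 14.7% to 49.4%.

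**3. Could the recorded count serve even if a POC-only group were available?** For any such comparison,

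recorded ratio = true rate ratio × (detection with CGM ÷ detection with POC alone).

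The documents give none of these inputs, so all values here are assumptions. Take 20 true episodes without CGM, 14 with it (true ratio 0.70), and 90% detection under CGM. Recorded episodes with CGM are 14 × 0.90 = 12.6.

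| Assumed POC detection | Recorded without CGM | Recorded ratio |
|---|---|---|
| 40% | 20 × 0.40 = 8 | 12.6 ÷ 8 = 1.58 |
| 63% | 20 × 0.63 = 12.6 | 12.6 ÷ 12.6 = 1.00 |
| 80% | 20 × 0.80 = 16 | 12.6 ÷ 16 = 0.79 |

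The same true 30% reduction can appear as a 58% rise, no change, or a 21% fall. Two further cases:

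- With no true effect, the recorded ratio is 0.90 ÷ 0.70 = 1.29 for detection of 90% against 70%, and 1.00 ÷ 0.50 = 2.0 for 100% against 50%.
- With 100% against 50% detection, a true halving gives 0.50 × 2.0 = 1.0.

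The recorded ratio equals the true one only when detection is equal in both settings.

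**4. Would splitting the 30 patients help?** The proportions with at least one event are again assumed, with two-sided alpha 0.05, 80% power and 1:1 allocation. The formula is n per arm = [1.96√(2p̄(1−p̄)) + 0.84√(p₁(1−p₁) + p₂(1−p₂))]² ÷ (p₁−p₂)². For 50% versus 25% this is (1.342 + 0.557)² ÷ 0.0625 = 57.7, so 58 per arm. The same formula gives 82 for 40% versus 20%, and 121 for 30% versus 15%. With 15 per arm, power in these three cases is about 29%, 22% and 16%.

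**The case against.** The strongest reply is that the only formal hypothesis is about identification, that the study calls itself a pilot, and that the word decrease is loose phrasing. Part of this stands. The pilot label excuses the missing power analysis. With POC and CGM running in the same women, a within-patient comparison for the hypothesis is conceivable. But the decrease aim appears twice, once in the section that justifies the study size, and a test at P < .05 is planned. A pilot label does not supply a comparator.

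Three stronger readings are tempting, and the documents do not support them.

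- A reader might infer that the study is declared single-arm. It is not. The absence of a control is inferred from the procedures, and the planned chi-square implies some comparison. The supportable statement is that no comparator is described.
- A reader might infer that better detection must raise the recorded count, so that CGM would look harmful. Alarms for impending hypoglycemia may prevent events, and the sign in the illustration reverses once POC detection exceeds 63%. Without a comparator, this study cannot form the ratio at all.
- A reader might infer that a change of wording is enough. The listed variables do not distinguish scheduled from alarm-triggered finger sticks and do not include monitoring time. An ordinary chi-square also ignores that both methods are applied to the same women.

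**Conclusion.** The concern holds. The stated aim and the hypothesis are different questions, and the plan as written cannot support a conclusion that CGM decreases hypoglycemic episodes. Enrolling more women in the same way, or choosing another test, would not change that. The recorded event count cannot be read as an effect in either direction. The range of 0.79 to 1.58 for a true 30% reduction only illustrates this; it rests on assumed event and detection rates and predicts nothing about this trial.

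The conclusion assumes that the procedures describe everyone who enrolls and that no comparison group exists outside the document. If one does, the plan must state it and show that events are ascertained in the same way in both groups. The detection hypothesis remains open to study in these 30 women, given the data and analysis changes below.

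**What to change.** 1. Reword the title, the aim and the sample-size sentence as the detection question, in line with the hypothesis. State that the design supports no conclusion about a reduction in hypoglycemia.
2. Record for each finger stick whether it was scheduled or prompted by a CGM alarm.
3. For each woman, classify whether POC-confirmed hypoglycemia was found by CGM alarm, by scheduled POC, by both or by neither. Compare the two proportions with a paired method such as exact McNemar in place of the ordinary chi-square.
4. Record monitoring time, and report events and treatments per patient-day descriptively, as inputs for a later controlled trial.
5. State as a limitation that acting on an alarm can alter later scheduled POC readings, so the detection comparison is itself affected by CGM-guided care.

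The cost is a narrower claim, one added data field per finger stick, recorded monitoring time and a changed test. No patients or procedures are added.

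### Alarm-triggered fingersticks are not separated from routine POC tests in the listed data or analysis, so the CGM-versus-POC contrast cannot be drawn from the variables as listed

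*Combined protocol and SAP*

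**What the plan says.** The Research hypothesis section states that CGM "is more effective at identifying patients with hypoglycemia than the traditional point of care (POC) blood glucose testing". No control arm is described, so the only comparator available is POC testing in the women who also wear the sensor. The sample is 30 patients, chosen for feasibility.

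The nursing-monitoring paragraph (in the procedures that follow Patient recruitment) describes two kinds of fingerstick. The first is routine: "Nursing will continue to perform standard POC blood glucose monitoring per routine protocol". The second is additional: nursing "will also obtain a finger stick to validate a blood glucose level whenever a low CGM alarm sounds". CGM is not masked: "Nursing will be able to see current glucose data on their patient and would receive alarms to indicate hypoglycemia or impending hypoglycemia". A glucose threshold appears only as a treatment trigger: "Low blood glucose values <70 mg/dl will be treated per hospital nursing policy".

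Data collection and analysis states: "Data variables to be collected include the type of diabetes (DM1/DM2), POC glucose values, number of hypoglycemic events, number of times treated for hypoglycemia". Hypoglycemic events are to be compared by chi-square at the 0.05 level. The section does not define an event, say which method is credited with it, or say which fingersticks form the POC comparator.

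**The concern.** A fingerstick taken because the sensor alarmed is a POC test in form, but CGM prompted it. The procedures keep it apart from routine testing; the data list and analysis do not. If both kinds enter one POC variable, the comparator is credited with what CGM found, and a real CGM advantage would be hidden or shown with the wrong sign.

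Removing the alarm-triggered tests is not a clean repair either. A low that is found by alarm and treated may have resolved before the next routine check, which might otherwise have found it. That favours CGM. The plan therefore needs both the label on each test and a stated way of handling this pre-emption.

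**Working it through.** The plan gives no calculated figure on this point to reproduce. The check has two parts.

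**1. What follows from the structure alone**

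Classify each patient by CGM-confirmed (yes/no) and POC-detected (yes/no). Suppose that:
- a CGM identification is a low alarm confirmed by fingerstick; and
- POC-detected means any low fingerstick, whatever prompted it.

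The confirming fingerstick makes every CGM-confirmed patient POC-detected, so the CGM-only cell is 0. CGM minus POC then equals minus the number of patients found by routine POC but not by CGM. That is zero or negative for any sensitivities, and it needs neither independence nor an outside figure.

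**2. Illustrative size**

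The documents give no detection rates. Assumed, per affected patient: routine POC s_POC = 0.30 to 0.50, CGM s_CGM = 0.80 to 0.90, detecting independently.

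- True difference = s_CGM - s_POC. Lowest: 0.80 - 0.50 = +0.30. Highest: 0.90 - 0.30 = +0.60.
- Pooled POC = 1 - (1 - s_POC)(1 - s_CGM). Lowest: 1 - 0.70 x 0.20 = 0.86. Highest: 1 - 0.50 x 0.10 = 0.95.
- Apparent difference = s_CGM - pooled POC = -(1 - s_CGM) x s_POC. Smallest: -0.10 x 0.30 = -0.03. Largest: -0.20 x 0.50 = -0.10.

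In patients, with n = 30, half having a low (assumed), s_CGM = 0.90 and s_POC = 0.40:

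| Quantity | Separated | Pooled |
|---|---|---|
| CGM-identified | 15 x 0.90 = 13.5 | 13.5 |
| POC-identified | 15 x 0.40 = 6.0 | 15 x 0.94 = 14.1 |
| CGM only | 15 x 0.90 x 0.60 = 8.1 | 0 |
| POC only | 15 x 0.10 x 0.40 = 0.6 | 0.6 |
| CGM minus POC | +7.5 | -0.6 |
| Exact McNemar power to show CGM better (two-sided 0.05) | about 69% | 0 |

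Exact McNemar needs at least 6 discordant patients, all in one direction, to reach 0.05 (2 x 0.5^6 = 0.031; with 5, 2 x 0.5^5 = 0.0625).

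Power after separation depends heavily on the assumptions. With 30% having a low, CGM at 80% and POC at 50%, it is about 7%. With 70% having a low, CGM at 90% and POC at 40%, it is about 89%. In the pooled analysis it is 0 in every case.

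**The case against.** Several stronger readings are tempting, and the documents do not support them.

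- **That the protocol instructs pooling.** It does not. The hypothesis says traditional POC, and the procedures describe the alarm fingerstick as additional and for validation. A natural reading is that routine checks are the comparator and the alarm fingerstick is the reference test for CGM. What stands is that no listed variable or analysis rule carries that separation through.
- **That no trigger field exists.** The data list is introduced with the word include, so it may not be exhaustive, and no data-collection form is among the documents. The supportable statement is that none is listed.
- **That the loss is irreparable.** CGM values are uploaded to a vendor website, and time-matching might recover the split. But no matching is planned, fingerstick times are not listed, and the key linking study ID to medical record is to be destroyed at the end of the project. Recovery is uncertain, not impossible.
- **That the trial could not show a CGM advantage under any definition.** The zero cell holds only for fingerstick-confirmed lows. If a sensor low alone counted, CGM could exceed POC, but the excess would be unconfirmed readings. Events are undefined, so the plan does not settle this.
- **That the percentage-point figures are evidence of a sign reversal.** They illustrate an identity on assumed inputs. Once pooling is assumed, the result is never positive.

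It is also fair to say that this is a pilot without a power analysis, and that separation does not guarantee a positive result at n = 30. Low power is acceptable in a pilot. A contrast that cannot favour CGM is a different fault, because more patients would not cure it.

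**Conclusion.** The concern holds in conditional form. The separation between routine and alarm-triggered fingersticks is made in the procedures but not carried into the listed data or the analysis, so the stated contrast cannot be drawn from the listed variables. Confidence in that gap is high, because it rests on the text alone.

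The collapse of the contrast rests on two conditions: that all fingersticks are analysed as POC, and that a CGM identification means a confirmed low. Given both, the difference is at or below zero. The deficit of 3 to 10 points, against a true +30 to +60, rests further on the assumed detection rates and on independence. This is a change to what the trial can conclude, not a wording matter, and it should be made while the reason for each test can still be recorded.

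**What to change.** 1. **Record for each fingerstick:** date and time; trigger (scheduled, CGM alarm or symptoms); paired CGM value or alarm status; and, for scheduled checks, the time the check was due. The due time is needed for step 4 and cannot be derived from the protocol, which gives no routine schedule.
2. **Define the two methods for analysis.** Comparator: a scheduled or symptom-prompted POC value below 70 mg/dL, the figure already in the protocol. CGM identification: a sensor low or alarm confirmed by any paired fingerstick below 70 mg/dL, including a scheduled one, so that CGM is credited when both methods see the same low. State the time window for pairing.
3. **Compare patients identified by each method with a paired analysis** (exact McNemar), in place of the chi-square, because both methods are applied to the same women.
4. **Add a sensitivity analysis** that also credits POC with any alarm-confirmed low for which a scheduled check was due within 30 minutes, and again within 60 minutes. These windows are a judgement, not figures from the documents.
5. **State as limitations** that nursing sees CGM values, so routine and symptom-prompted checks are not independent of CGM, and that treatment after an alarm can pre-empt routine detection, which favours CGM.

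Cost: staff log a few extra items per fingerstick, and the analysis section gains a short paragraph. Testing, nursing response and number of patients do not change. These are definitions for analysis only and have no bearing on when lows are treated.

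### Nothing in the plan separates alarm-triggered finger sticks from routine POC checks, so a mean of all POC values would lie below the scheduled-check glucose level, by an amount the documents do not give

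*Combined protocol and SAP*

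**What the plan says.** The nursing-monitoring paragraph (under Patient recruitment) sets up two reasons for taking a finger stick. The first is the usual schedule: "Nursing will continue to perform standard POC blood glucose monitoring per routine protocol". The second is the sensor: nursing "will also obtain a finger stick to validate a blood glucose level whenever a low CGM alarm sounds". The alarms in question are those that nurses "would receive alarms to indicate hypoglycemia or impending hypoglycemia".

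Data collection and analysis lists, besides type of diabetes, "POC glucose values, number of hypoglycemic events, number of times treated for hypoglycemia". It names no field for the time of a reading or the reason for it. The analysis sentence is "Continuous variables will be analyzed using a fishers exact t-test (i.e. blood sugar measurements", followed by a .05 significance threshold. It does not say which readings enter, whether the unit is the reading or the woman, or which groups are compared.

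The Research hypothesis is that CGM "is more effective at identifying patients with hypoglycemia than the traditional point of care (POC) blood glucose testing".

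**The concern.** A scheduled check is taken whatever the glucose happens to be. An alarm check is taken because the sensor already reads low or is heading there. If both go into one variable, the chance that a value is recorded depends on the value itself, and low values are over-represented. Replacing the misnamed test with a valid one would not cure this. Nor would reducing each woman to one mean, because the distortion lies in which values were recorded.

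Two things are at stake. First, a POC mean would understate glucose as the routine schedule measures it, and a comparison between groups that alarm at different rates could show a difference produced by the extra testing. Type of diabetes is the only grouping variable listed, so type 1 versus type 2 is the obvious candidate if a comparison is made. Second, a low found only because the sensor alarmed would be stored as a POC value below 70 mg/dl. Without a label it could not later be told apart from a low that routine testing found unaided, and that distinction is what the hypothesis turns on.

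**Working it through.** **What the documents supply.** One extra stick per low alarm, a low threshold of <70 mg/dl, one POC glucose variable, a .05 threshold and 30 women. They do not give the number of routine checks, the alarm setting, the alarm rate or any glucose mean or SD. The sample size rests on feasibility, so there is no calculation to reproduce. Everything below that needs a missing input uses an assumed one.

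**Direction.** For one woman,

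pooled mean − scheduled mean = −[n_alarm / (n_sched + n_alarm)] × (mean_sched − mean_alarm).

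This is negative whenever alarm sticks average lower than scheduled checks, which is what their trigger leads one to expect.

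**Size for one woman** (assumed: 12 scheduled sticks at mean 120 mg/dl, 4 alarm sticks):
- alarm mean 65: −(4/16) × 55 = −13.75 mg/dl
- alarm mean 85: −(4/16) × 35 = −8.75 mg/dl

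**Gradient** (alarm mean 70): the shift is −3.8 mg/dl with 1 alarm, −7.1 with 2, −12.5 with 4 and −20.0 with 8. The order can reverse if frequent alarmers have a small gap between scheduled and alarm values. One alarm at a gap of 60 gives (1/13) × 60 = 4.6. Six alarms give less than that only if the gap is under 4.6 / (6/18), about 14 mg/dl. Hence generally, not always.

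**Share of readings <70** (assumed: 1 of 12 scheduled readings low, or 8%; alarm-stick SD 8):
- alarm mean 65: 73% of alarm sticks are <70, so (1 + 4 × 0.73)/16 = about 25%
- alarm mean 85: 3% are <70, so (1 + 4 × 0.03)/16 = 7%. With an SD of 12 it is 11%, giving 9%.

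The share of lows therefore rises sharply only if most alarm sticks confirm a low. At an alarm mean of 85 it hardly moves.

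**Group comparison** (simulated; assumed: 12 versus 18 women with identical scheduled glucose, mean 120, between-woman SD 15, within-woman SD 30, Poisson alarm counts, alarm-stick SD 8, two-sample t-test on one mean per woman). Rejection at P<.05, with ranges showing the spread over repeat runs:

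| Scheduled sticks | Mean alarm sticks, group A v B | Alarm mean 65 | 75 | 85 |
|---|---|---|---|---|
| 12 | 4 v 1 | 32–34% | 23–24% | 15–16% |
| 12 | 3 v 1 | 17–18% | 13% | 10% |
| 12 | 2 v 1 | 8–9% | 7% | 6% |
| 12 | equal (1 v 1, 2 v 2) | 5% | 5% | 5% |
| 20 | 4 v 1 | 19% | 12–14% | 10% |

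Using scheduled values only, rejection is about 5% throughout. With 12 scheduled sticks and 4 v 1 alarms, the spurious gap is about 9, 7 and 6 mg/dl at alarm means of 65, 75 and 85.

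**The case against.** The strongest reply is that the plan never says the two kinds of reading are pooled. Its variable list is introduced as what the data include, so it need not be exhaustive. Alarm sticks have a stated validating purpose, and the traditional POC testing of the hypothesis could mean routine checks alone. This stands as far as it goes: pooling is inferred from one undivided variable and the absence of any separating rule. But an alarm finger stick is a POC glucose value, and nothing in the text keeps it out.

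Second, a reader might infer that every glucose comparison in the study is distorted. The documents do not support that. They describe one cohort in which every woman wears a sensor. They name no groups and no target quantity for blood sugar, and they do not list CGM values among the variables to be collected. In the simulation, equal alarm rates produce no excess false positives.

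Third, a false-positive rate of about one third might be read as a property of this trial. It is not. The 12 versus 18 split, the alarm counts and the alarm mean are all assumptions. Because alarms also sound for impending lows, a mean of 65 is towards the severe end. Moreover, a group with more true alarms may really have more lows between scheduled checks. The rejections are false only relative to scheduled-check glucose, a target the plan does not name.

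Finally, mean blood sugar is secondary to hypoglycemia in an unpowered pilot of 30. That is fair, but the plan still tests it at .05, and the missing label also affects the main question.

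**Conclusion.** The concern holds as a gap in the plan with a predictable direction. Followed as written, the plan would mix value-triggered readings with scheduled ones, lower the POC mean relative to the scheduled-check level, and generally lower it most in women who alarm most. The mixing is inferred, not stated.

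The size cannot be read from the documents. It is about 9 to 14 mg/dl for a woman with four alarm sticks on top of 12 scheduled ones, under the assumed means. Inflation of the error rate arises only if groups with unequal alarm rates are compared. With 12 scheduled sticks it ranges from slight (6 to 9% at two versus one) to substantial (15 to 34% at four versus one), and it is smaller with more scheduled checks. The loss of attribution between CGM-found and POC-found lows depends on none of these numbers, only on the absence of a label. The plan should be corrected on this point.

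**What to change.** In Data collection and analysis:
- Record for each POC value its time and its reason: scheduled, alarm-triggered or other unscheduled.
- State that the blood sugar analysis uses scheduled values only.
- Report alarm-triggered values separately, as confirmation of CGM alarms. In the hypoglycemia analysis, use the label to show which lows came from a scheduled check and which only from an alarm.

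The reason should be captured when the stick is taken. The key linking study numbers to medical records is to be destroyed at the end of the project, after which it could not be recovered from the chart.

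The cost is a small addition to the REDCap form, a sentence or two of analysis text, and fewer POC values in the glucose-level summary. Clinical care is unchanged.

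### A hypoglycemic event is given no definition and no source method, so an ordinary chi-square on events would treat repeated, same-patient data as independent and mix CGM-prompted fingersticks into the POC comparator

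*Combined protocol and SAP*

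**What the plan says.** The research hypothesis is that CGM "is more effective at identifying patients with hypoglycemia than the traditional point of care (POC) blood glucose testing". The title and the section on number of subjects state the aim as fewer hypoglycemic episodes or events. No outcome is designated as primary.

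The section Data collection and analysis lists "number of hypoglycemic events" by name only. It then says: "Categorical variables will be compared using a chi square analysis (i.e. hypoglycemic events"), at a 0.05 level. It does not say which groups are compared. Its variable list includes POC glucose values but not CGM values, although CGM readings are uploaded to the manufacturer's website.

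The nursing procedures, which follow under Patient recruitment, describe both methods running together. "Nursing will continue to perform standard POC blood glucose monitoring per routine protocol", and nurses "would receive alarms to indicate hypoglycemia or impending hypoglycemia" and "will also obtain a finger stick to validate a blood glucose level whenever a low CGM alarm sounds". The only glucose threshold is a treatment trigger: "Low blood glucose values <70 mg/dl will be treated per hospital nursing policy". No separate control group is described, so both methods appear to be applied to the same patients.

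**The concern.** Four different records could each be called an event: a CGM reading below 70 mg/dl, a CGM alarm, a stick taken because of an alarm, or a scheduled POC value below 70 mg/dl. There is no minimum duration, no rule for when one event ends and the next begins, and no rule for repeat alarms or repeat sticks during one low.

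This affects the analysis in three ways.

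- **The count depends on the rule.** If the rule is chosen after the data are seen, the result can depend on that choice.
- **The test assumes independence.** Repeated events within one low, several lows in one patient, and two methods in one patient all violate the assumption of an ordinary chi-square.
- **The comparator is contaminated.** A stick taken because CGM alarmed is a POC value in the record. Unless it is tagged, a low that CGM found is credited to POC.

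At stake is whether this 30-patient pilot can give an interpretable estimate of how many patients or episodes each method finds.

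**Working it through.** The plan gives no event rate, episode duration, CGM reading interval or POC schedule, so it has no figure to reproduce. The numbers below are illustrations. Assumed throughout: error-free methods and a CGM reading every 5 minutes. Other assumptions are stated at each step.

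**1. How far the count depends on the rule.** Simulated 48-hour traces (3,000 stays; mean 115, SD 25 mg/dl, correlation time 90 minutes, cut-off below 70) were counted in several ways:

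| Rule | Mean events per stay | Share of stays with any |
|---|---|---|
| Every CGM reading below 70 | 20.4 | 0.955 |
| Every run of low readings | 5.9 | 0.955 |
| Runs of at least 15 min | 2.3 | 0.825 |
| Same, with 15-min separation | 2.05 | 0.825 |
| Scheduled POC every 4 h | 0.41 | 0.346 |
| Scheduled POC every 6 h | 0.30 | 0.258 |

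The CGM count varies by 20.4/2.05, about 10-fold. The share of stays with any CGM event varies only by 0.955/0.825, about 1.16-fold. The exact ratios depend on the assumed trace.

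**2. Reading-level counts inflate CGM.** Assume 20 lows of 30 minutes, each found by both methods, with one repeat stick per low. CGM gives 20 × 30/5 = 120 low values and POC gives 20 × 2 = 40. That is 3:1 when true detection is 1:1.

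**3. Untagged alarm sticks inflate POC.** Assume 20 lows of 60 minutes and scheduled POC every 4 hours. Scheduled sticks catch a share 60/240 = 0.25, or 5 lows, so CGM to scheduled POC is 20:5. If every low also sets off an alarm and the alarm stick confirms it, all 20 lows have a POC value below 70. Untagged, the ratio is 20:20, and the contrast disappears.

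**4. The denominator can reverse the direction.** A chi-square needs one and the plan names none. With 30 patients, 48 hours and POC every 4 hours, there are 30 × 48 × 12 = 17,280 CGM values and 30 × 12 = 360 scheduled sticks. Using the counts from step 2, CGM is 120/17,280 = 0.7% low and POC is 40/360 = 11% low (40/380 = 10.5% if the 20 repeat sticks are added).

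**5. Dependence.** The design effect is 1 + (m − 1)ρ. With ρ = 1 within a low and m = 6 CGM readings, the standard error is understated by √6 = 2.45. For POC with m = 2 it is √2 = 1.41. Each factor applies to its own method, and neither is the error in the comparison. At patient level there is no repeat counting, but the same patient still contributes to both methods, so the data are paired.

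**6. What a common rule leaves in place.** After the 15-minute rule, step 1 still gives 2.05/0.41 = 5:1 or 2.05/0.30 = 6.8:1. At patient level, assume one 60-minute episode per stay on average and 4-hourly POC. CGM flags 30 × (1 − e^−1) = 19.0 patients and scheduled POC flags 30 × (1 − e^−0.25) = 6.6. This remainder comes from sampling frequency, and part of it is what CGM offers.

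**The case against.** The strongest reply is that this is a definition gap in a small pilot and not a demonstrated bias. The hypothesis is about identifying patients, and a chi-square for categorical variables fits a yes/no per patient at least as well as a count. On that reading repeat values within a low change nothing. The alarm stick that validates a CGM low could be the basis of a blood-confirmed event. Frequent sampling is also the reason CGM might find more patients.

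Much of this stands. The patient-level reading is reasonable and the fix adopts it. The plan does not state it, however: the variable is listed as a number, and no rule says that only confirmed lows count. Even at patient level, an ordinary chi-square ignores the pairing, and untagged alarm sticks still enter the POC side.

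A reader might also infer three stronger things that the documents do not support:

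- *That an event count is the main outcome.* No primary outcome is named, and the groups for the chi-square are not stated.
- *That the plan builds in a bias towards CGM.* Steps 2 to 4 show that the direction depends on the rule, the tagging and the denominator. An understated standard error raises false rejection in either direction.
- *That 3:1 or 2.4-fold is the expected error.* Both hold only if single readings are counted as events, which the plan does not say.

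**Conclusion.** The concern holds as a fault in the analysis whose direction is unknown. Followed as written, the plan permits an ordinary chi-square on repeated, same-patient events with CGM-prompted sticks mixed into the comparator. That test and that contrast would not be sound. The count's dependence on the rule is large (about 10-fold under the simulation's assumptions), while the patient-level any-event measure is much less sensitive to it. A difference that remains under a common rule should not be read as pure artefact, since denser sampling is partly a real advantage of CGM. The conclusion that the event is undefined and the data dependent rests on the text alone. Every size quoted rests on assumed intervals, durations and event rates.

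**What to change.** 1. **Define one episode before data are read**, for analysis only: values below 70 mg/dl, with a prespecified minimum CGM duration and separation interval. Fifteen minutes for each is an example, with 0 and 30 minutes as sensitivity analyses. Repeat alarms and repeat sticks within it count as one episode. Take CGM episodes from the glucose trace and not from alarms, which also cover impending lows.
2. **Extend the collected data.** Add time-stamped CGM values under the study ID, and tag each fingerstick as scheduled or alarm-triggered. Do this during the study, because the plan destroys the linking key at the end.
3. **Change the analysis.** Make the main comparison patients with at least one episode found by CGM versus by scheduled POC, as paired data with an exact McNemar test. Analyse episode counts with the patient as the cluster in place of an ordinary chi-square.

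Report the routine POC schedule beside the result, so that readers can see how much of any difference reflects sampling frequency. One limit remains: a low treated after an alarm stick may be over by the next scheduled stick, so scheduled POC in these patients may understate what POC alone would have found.

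The cost is a paragraph of analysis text, two extra data fields and some programming. Very brief CGM dips are left out of the main analysis but appear in the 0-minute sensitivity analysis. Treatment of lows is unchanged.
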